4.8.2. BPD as a Predictor of Forced Expiratory Flow (FEF-75) by iPFT

Our primary lung function outcome is the FEF75 measured at one year by RVRTC, in the unit of ml/s. The sample size for iPFTs is estimated based on this primary outcome, although we will also examine the relationship of various predictors and other lung function measures. Although factors other than a history of BPD may contribute to lower lung function at one year, we have chosen BPD for our sample size estimates because it is a well documented risk factor for lower lung function.¹⁵ Linear regression will be used to test the difference in FEF75 between PROP premature infants who have a history of BPD and those without, adjusting for weight, length, and other possible covariates.

Because there is no existing study that has investigated the difference in FEF75 between the infants with and without BPD, we will estimate our effect size from a cohort study that examined lung function and bronchodilator responsiveness between full term infants and preterm infants with a history of BPD.⁴¹ The time range (outcome measured at an average 68 week for preterm infants and 57 week for full term infants) and comparison groups (infants with and without BPD) are similar to this study. But in contrast to full or close to full term infants in that study, our comparison will be in preterm infants, which may lead to smaller differences.

In the Robin et al.'s study, the mean difference in FEF75 between two groups was 34.8% and the observed s.d. of FEF75 was about 30.7% and thus the estimated effect size is 1.1 SD (a moderate size). The prevalence of BPD is estimated to be 40% in infants born between 24 to 28 gestational weeks (SUPPORT Study Group¹²⁰). To judge the impact on sample size in the face of an observed prevalence different in our PROP cohort, we examined potential prevalence rates of BPD at 30%, 40%, and 50%. In addition to our conservative estimated dropout of 5% of the cohort (Section 4.4) from discharge, we will need to consider the ability to obtain high quality data for this outcome measure. The success rate in obtaining high quality research data is variable, ranging from 70-90%, which is highly associated with experience.⁹² Although all of the PROP sites that will be performing iPFTs are highly experienced, we will use a conservative 75% success rate. We have assumed a combined loss of data from both infant dropout and failure of testing that gives a cohort available and completing exams of 71.3%. It is estimated that approximately 50% of the parents will consent for their child to have iPFTs. In addition, only 5 of the sites will be performing iPFTs. The potential available sample size may be 600 (4 x 150) with little further reduction based on the exclusions outlined in Section 3.3.

The sample size required to obtain 80% power to detect a significant difference in the primary outcome between two groups for effect sizes ranging from 0.5SD (relative small effect) to 1.2SD (moderate effect) is shown in Figure 4.8.2. Sample size decreases dramatically with
decreasing OR, but is not highly sensitive to changes in the prevalence of BPD. If the prevalence of BPD is $40\%^{107}$ then with a size of 164, we will have 80% power of detecting a significant difference in FEF75 between two groups with an effect size 0.75 SD or more (a significant level of α = 0.05 using a two-tailed test (Table 4.8.2). A 0.75 SD difference between those infants with and without BPD would correspond to 23.0 (%) differences between two groups if we assume the same s.d. in our sample as in Robin et al.'s paper. For a smaller effect size of 0.5 SD, we will need a sample size of 368 to have 80% power. The above sample sizes are the initial sample sizes required at discharge and after considering the 5% post discharge mortality, the 50% consent rate, the 5% loss to follow-up rate and a 25% test failure rate, the effective sample sizes would be 56 and 125 for detecting a difference of 0.75 SD and 0.5SD, respectively. We have chosen to attempt 368 evaluations of FEF75 to be conservative. The potential for selection bias is discussed in Section 4.10.1.

Figure 4.8.2: Sample size required to obtain 80% power of detecting a difference in FEF75 between infants with and without BPD at a significance level of α = 0.05 (two tailed).

Effect Size (Group Difference)		BPD Prevalence			
In SD	In %	30%	40%	50%	
0.5 SD	15.4	420	368	354	
0.75 SD	23.0	188	164	158	
1 SD	30.7	106	92	90	

Table 4.8.2 Examples of sample sizes required to obtain 80% power of detecting a difference in FEF 75 between infants with and without BPD.

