Our target sample size of at least 180 studies will represent the largest number of RVRTC PFTs in the preterm population and will allow us to study the relationship between lung function at 1 year of age and clinical and biologic factors associated with respiratory disease.

Infant pulmonary function testing for PROP will proceed in the following order:

- 1. Tidal breathing analysis (which includes Tpef/Te)
- 2. Crs and Rrs (compliance and resistance)
- 3. FRC measurement using whole body plethysmography
- 4. Forced expiratory flows from raised volumes (FVC, FEV0.5, FEF25-75, FEF75)
- 5. Fractional lung volumes (ERV, TLC, RV/TLC, FRC/TLC)
- 6. Bronchodilator response (Forced expiratory flows from raised volumes)

Parents will be approached for the iPFT before the infant reaches 12 months corrected age. An infant will be excluded from PF Testing for the following reasons:

- 1. History of adverse reaction or allergy to chloral hydrate sedation
- 2. Current symptoms of nasal obstruction or discharge
- 3. Clinically significant upper airway obstruction as determined by the Site Investigator (e.g. severe laryngomalacia, markedly enlarged tonsils, significant snoring, diagnosed obstructive sleep apnea)
- 4. Severe gastroesophageal reflux, defined as persistent frequent emesis despite antireflux therapy
- 5. Acute intercurrent respiratory infection, defined as an increase in cough, wheezing, or respiratory rate with onset in 2 weeks preceding visit
- 6. Hydrocephalus
- 7. Congenital heart disease

- 8. Severe neuromuscular disease
- 9. Any physical findings or conditions that would compromise the safety of the infant or the quality of the study data as determined by site investigator.

The parents of all eligible PROP participants will be asked to consider PF Testing. A separate consent form will be administered at the time of the test to explain the risks and benefits.

3.3.4. **Risks of iPFT**

Performing infant PFTs includes the use of moderate sedation with oral or rectal chloral hydrate (CH). Potential side effects of CH include respiratory depression, gastritis, and paradoxical agitation. All CH sedation will be performed under local institutional sedation policies, which include having appropriate monitoring and the presence of appropriately trained individuals present in the event of an untoward event.

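### Section 4.8.2 adopts 368 infants at discharge as 368 tests to attempt, and sizes Table 4.8.2 with one 5% loss but its effective sample sizes with two

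*Protocol*

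**What the plan says.** Section 4.8.2 sizes the comparison of FEF75 between infants with and without BPD at 80% power, two-sided α = 0.05 and a planning BPD prevalence of 40%. For an effect of 0.75 SD it says that "with a size of 164, we will have 80% power of detecting a significant difference in FEF75 between two groups". For 0.5 SD it says: "For a smaller effect size of 0.5 SD, we will need a sample size of 368 to have 80% power".

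It explains that these are starting counts at discharge. After 5% mortality, 50% consent, 5% loss to follow-up and 25% test failure, "the effective sample sizes would be 56 and 125 for detecting a difference of 0.75 SD and 0.5SD, respectively". The next sentence reads: "We have chosen to attempt 368 evaluations of FEF75 to be conservative".

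Three other statements bear on this:

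- Earlier in Section 4.8.2, one 5% dropout and a 75% test success rate are combined into a loss that "gives a cohort available and completing exams of 71.3" percent.
- The same paragraph says that five sites will test and about half of parents will consent, and adds: "The potential available sample size may be 600 (4 x 150").
- Section 3.3.3 gives a different count: "Our target sample size of at least 180 studies".

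**The concern.** Two consecutive sentences give 368 two meanings: infants present before any loss, and tests carried out. The two differ by a factor of about 2.2. Section 3.3.3 does not say whether its 180 studies are attempted or usable, so it does not settle which meaning applies.

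The allowance for losses also changes within the section, from one 5% loss to two. If the table was built with the lighter allowance and the effective sizes with the heavier one, the stated 80% power does not belong to the stated effective sizes.

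At stake are the number of sedated, separately consented tests that sites should plan for, and the power that may be quoted for the main lung function comparison.

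**Working it through.** **Inputs (Section 4.8.2).** Two-sided α = 0.05, power 80%, BPD prevalence p = 0.40, effects d = 0.5 and 0.75 SD, consent 0.50, test success 0.75, one or two 5% losses, pool 600.

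**1. Reproduce the plan's figure.** Usable tests needed: N = (1.96 + 0.8416)² / (d² p(1−p)).

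- d = 0.5: N = 130.8, rounded up to 131.
- d = 0.75: N = 58.1, rounded up to 59.

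Retention with one 5% loss is 0.95 × 0.75 × 0.50 = 0.35625 (0.95 × 0.75 is the stated 71.3%). With two it is 0.95 × 0.95 × 0.75 × 0.50 = 0.3384.

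130.8 / 0.35625 = 367.2, or 131 / 0.35625 = 367.7, so 368 is reproduced. All of Table 4.8.2 behaves the same way:

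| Effect, BPD prevalence | Printed | One 5% loss | Two 5% losses |
|---|---|---|---|
| 0.5 SD, 30% | 420 | 419.7 | 441.7 |
| 0.5 SD, 40% | 368 | 367.2 | 386.5 |
| 0.5 SD, 50% | 354 | 352.5 | 371.1 |
| 0.75 SD, 30% | 188 | 186.5 | 196.3 |
| 0.75 SD, 40% | 164 | 163.2 | 171.8 |
| 0.75 SD, 50% | 158 | 156.7 | 164.9 |
| 1 SD, 30% | 106 | 104.9 | 110.4 |
| 1 SD, 40% | 92 | 91.8 | 96.6 |
| 1 SD, 50% | 90 | 88.1 | 92.8 |

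Every printed cell lies within 2 of the one-loss value. None matches the two-loss value.

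**2. The effective sizes.** 368 × 0.3384 = 124.5 and 164 × 0.3384 = 55.5. These are the stated 125 and 56, so they carry two 5% losses. With the table's own retention they would be 368 × 0.35625 = 131.1 and 164 × 0.35625 = 58.4.

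**3. Power at the stated effective sizes, p = 0.40.** Normal formula: Φ(d √(N p(1−p)) − 1.96).

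- N = 125, d = 0.5: Φ(2.739 − 1.96) = 78.2%; non-central t gives 77.6%.
- N = 56, d = 0.75: Φ(2.750 − 1.96) = 78.5%; non-central t gives 77.0%.

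**4. 368 read as infants at discharge.** 368 × 0.50 = 184 consent. After one 5% loss 174.8 are testable, after two 166.1. The last figure × 0.75 gives about 125 usable tests. This fits within 600 and is close to 180. If the 180 are attempts, 180 × 0.75 = 135 usable tests, with power 81.2% (80.7% by t).

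**5. 368 read as tests attempted.** The pool gives 600 × 0.50 = 300 consenting, 285 after one 5% loss and 271 after two. To attempt 368 would take 368 / 0.475 = 775 infants with one loss, or 368 / 0.45125 = 816 with two; the whole cohort is 750. If 368 attempts were possible, 368 × 0.75 = 276 usable tests would give about 98% power.

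**The case against.** The best defence is that the intent is clear and the sub-study is not at risk. Read as infants at discharge, 368 follows correctly from the inputs in Section 4.8.2, fits within 600 and roughly agrees with 180 studies, which is a floor. Section 3.3.3 says all eligible families will be asked. If all 600 infants were approached, 600 × 0.3384 = 203 usable tests would give about 94% power at 0.5 SD with 40% BPD. This stands, and it limits the seriousness. It does not remove the unit error in the sentence that sets the number of tests, or the change of loss allowance.

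Three stronger readings are tempting but not supported:

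- **That 368 both exceeds supply and misses 80% power.** The first needs 368 to be attempts, where power would be about 98%. The second needs it to be infants at discharge, where supply is ample. No single reading gives both.
- **That 368 is not conservative because the 30% prevalence cell is 420.** The surrounding sentences contrast 0.5 SD with 0.75 SD at 40% prevalence, against an estimated effect of 1.1 SD. Choosing 0.5 SD is a reasonable meaning of the word.
- **That the pool should be 625.** Five of six centres at 125 each assumes equal accrual, which the protocol does not state. What can be said is that a product of 4 and 150 sits unexplained beside five testing sites.

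**Conclusion.** The point holds as two separate inconsistencies. First, the number of tests to attempt is given in the wrong unit: 368 infants at discharge correspond to about 166 attempts (about 175 with one 5% loss), and 368 attempts cannot be drawn from 600 infants at 50% consent. Second, the table and the effective sizes use different loss allowances, so 125 and 56 usable tests carry about 78% power, not 80%. That shortfall is 1.5 to 1.8 points by the table's own formula and 2.4 to 3.0 points by the t distribution, and it arises only through the second 5% loss.

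These results take the protocol's consent, loss and success rates as given and treat the comparison as an unadjusted two-group difference, which reproduces the table. The importance is moderate: the primary outcome and the cohort of 750 are unaffected.

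**What to change.** 1. Use one set of units in Sections 3.3.3 and 4.8.2: infants at discharge, tests attempted, usable tests. Replace the sentence on attempting 368 evaluations with the number of infants and the attempted and usable tests that follow. Say which of these the 180 counts.
2. Apply one loss allowance throughout. Either keep the single 5% loss and correct the effective sizes to about 131 and 59, or keep both 5% losses and restate the 40% column of Table 4.8.2 as about 387, 172 and 97, with the other columns recomputed likewise. A third option is to keep 368 with both losses and state about 78% power. Sections 4.4.1 and 4.8.1 already allow for deaths and loss to follow-up separately, which favours two losses, but the choice is the sponsor's.
3. Name the formula. The 131 reaches 80% by the normal approximation; by the t distribution it gives 79.5%, and 133 usable tests are needed.
4. Reconcile the 600, written as a product of 4 and 150, with the five testing sites, or explain the product.

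The cost is corrected text and, under one option, a recomputed table. No extra enrolment is needed, since even 387 infants lie within the stated 600.

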4.9. Validation of Models and Biomarkers

It is generally the case that model building within a data set (derivation set) will produce results superior to those when the model is applied to an independent data set (test set), one not used in building the original model. It is expected that model building in the PROP cohort will involve the assessment of one or more markers independently and in conjunction with each other and with

consideration of other factors such as gender, birth weight, and gestational age at birth. While these complex models can be assessed in a sample held back from the original sample for use as a test sample, this approach will reduce the reliability of our statistical testing procedures due to the decrease in sample size in the sample used to derive the model. After deriving the primary base model, we will then use 10-fold cross validation to evaluate the predictive accuracy of the candidate final model.

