4.1. Global Objectives

The global objectives of PROP are the investigation of hypotheses on the molecular mechanisms that contribute to respiratory disease risk of the premature newborn with the long-term goal of improving outcomes in the first year of life. More specifically the study design allows for the assessment of hypotheses of pathophysiological mechanisms and biomarkers that will characterize preterm infants and predict respiratory morbidity in several domains including medical resource utilization and respiratory symptoms over time and physiological and other measures at one year. PROP is a hypothesis generating multicenter study with myriad candidate predictors with the

longitudinal nature of the study allowing for the assessment of risk modification over time. Our development of the Statistical Considerations section will start with an examination of the primary outcome and main secondary outcomes. These sections will be followed by discussion of general power considerations, analytic approaches and more general statistical issues such as causal pathways, multiple comparisons, selection bias, and issues in generalization.

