4.4. Power Considerations

Since the sample size of 750 participants was established by the RFA, discussion of power will be in the context of this fixed sample size for the primary outcome. We have made assumptions concerning loss to follow-up due to death and non illness related departures. As will be seen, the sample size is adequate to provide appropriate power for all of the examples presented below, which should account for reasonable departures from our assumptions, without losses of sensitivity to detect meaningful differences.

4.4.1. **Primary Outcome**

Our primary outcome PRD is binary and we will use logistic regression models to test the correlation between a biomarker and the outcome. With current sample size, we consider a range of PRD rates from 30% to 50%, allowing us to conceive a possible range of power. We also let the odds ratios (OR) for the change of one standard deviation in the biomarker vary from 1.2 (small effect) to 1.6 (moderate effect). Assuming no measurement errors and no correlation between the biomarker and other covariates, Figure 4.4.1 shows the power to detect various odds ratios for the possible outcome with PRD rates of 30%, 40% and 50% at $\alpha = 0.05$ using a two-tailed test.

Because the power is the same for any two PRD rates symmetric around 50% (e.g., 40% and 60%), we only show the power for PRD rates up to 50%. Power increases as the PRD rate and the minimum detectable odds ratio increase. For a PRD rate of 40%, given a sample size of 750 and a conservative missing rate of 10% (5% due to late deaths and 5% due to loss to follow up), we will have sufficient power (>80%) to detect a significant biomarker-PRD association at OR of 1.25 or higher for one S.D. increase in the biomarker.

Odds Ratio for One SD Change of the Biomarker Variable

Figure 4.4.1: Power of detecting a significant association between a biomarker and the binary outcomes for various odds ratios at a significance level of α =0.05 assuming a missing rate of 10%.

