4.6. General Statistical Analytic Approaches

Most standard hypothesis tests will be specified as using a two-sided significance level (Type I error) of α = 0.05, although actual p-values will be reported whenever possible. For measured continuous variables, two-group comparisons will generally employ Wilcoxon rank-sum tests to protect against violations of normality assumptions. The Wilcoxon test affords little loss of power, as it is more than 95% efficient with respect to the two-sample t-test when normality holds. Similarly, Wilcoxon signed-rank tests will be used for paired data and Kruskal-Wallis tests will be used for k-group comparisons. In some instances, t-tests and analysis of variance (ANOVA) methods may be used to facilitate group comparisons when the appropriate assumptions are met. Categorical variables,

including dichotomous factors, will be summarized by proportions and compared among groups using standard chi-square tests of association and generalized Mantel-Haenszel (MH) methods, as described in Landis et al¹⁰⁶ to accommodate both nominal and ordinal measurement scales. These MH methods are useful for adjusting primary associations for potential confounders. Whenever possible, exact p-values from Exact Conditional Tests, such as Fisher's exact test and its multidegree of freedom extensions, will be produced for these tests.

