4.6.1. Univariate Models

Candidate biomarkers for inclusion in multivariate modeling will be assessed using marginal models or simple two way analyses, depending on the structure of the biomarker, to ascertain predictive value, if any. At this stage of model selection, factors will be moved forward for further evaluation if either their predictive value produces a p value of \leq 20% or they are biomarkers supported in the literature.

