4.6.4. Multiple Comparisons

The analysis approaches described will likely involve a great number of individual statistical tests at both the univariate and multivariate levels. In some cases we utilize global statistical testing (e.g. omnibus contingency table assessments prior to marginal assessments). In other cases it will be appropriate to provide some protection against detecting false positive results by using a stepwise modeling procedure which enters and removes covariates based on

threshold values of p<0.15 and p<0.10 (or otherwise specified in the protocol), respectively, to initially reduce the number of candidate factors.¹¹¹ We are choosing to generally avoid severe adjustments of significance levels using multiple comparison techniques, which would lessen the chance of detecting potentially important biomarkers and other risk factors for severity of respiratory disease.¹¹² We take these more liberal approaches to dealing with multiple comparisons because PROP, an observational study, is considered a hypothesis generating rather than hypothesis testing study. Thus we will generally report significance values related to odds ratios for biomarker prediction of one year outcome as indicators for risk factors that are candidates for confirmation in future studies.

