4.7. Specific Analytic Approaches

The specific analytic approaches to the assessment of which biomarkers play an important role in the prediction of one-year outcome will be discussed. The following sections provide a brief overview of some of the statistical methodologies and considerations that will be used at the time of analysis, both for descriptive purposes, and univariate and multivariate analyses relating biomarkers to one-year outcome(s). For a large study with many exposures or predictors, several outcome variables, and many scientific questions of interest, some of which will evolve with analysis itself, it is not possible to detail analyses of each question. Nonetheless, the types of analyses described here are likely to be used to answer many of the questions that arise. We consider here the principal methodological issues and approaches for dealing with those issues.

4.7.1. **Prediction of Outcome**

The primary focus of PROP is on the delineation of early biomarkers during the NICU hospitalization period that predict *respiratory morbidity through 1 year of age*. We have chosen to approach the assessment of this hypothesis using mixed effect logistic regression, Preliminary analyses will provide a parsimonious set of predictors to be considered in multivariate analyses. A full model will include all main effects (fixed) of parsimonious predictors and a random effect reflecting ICN variation and we will use variable selection techniques such as AIC, BIC and LASSO to select a subset of predictors as a candidate prediction model. All higher-order and interaction terms will be considered as well if there is any indication of effect modifier or non additive effects. For repeated measures, we will use generalized estimating equations (GEE¹¹³) for prediction of the outcome that can be implemented in SAS GENMOD procedure.

Center and Site Variability

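### Section 4.9 cross-validates a model whose predictors were already selected on the whole cohort, so the cross-validated accuracy is biased upward and does not remove the optimism the section sets out to address

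*Protocol*

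**What the plan says.** The Protocol describes model building in several steps, each of which uses the outcome.

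- Section 4.6.1 (univariate models): "factors will be moved forward for further evaluation if either their predictive value produces a p value of" 20% or less, or if the literature supports the marker.
- Section 4.6.4 (multiple comparisons): in some cases the plan will "provide some protection against detecting false positive results by using a stepwise modeling procedure", with entry at p<0.15 and removal at p<0.10, to cut the number of candidates.
- Section 4.7.1 (prediction of outcome): from a preliminary reduced set, "we will use variable selection techniques such as AIC, BIC and LASSO to select a subset of predictors as a candidate prediction model". Interactions and higher-order terms are considered if the data suggest them.
- Section 4.9 (validation): it recognises that a model looks better in the data that built it than in independent data. It declines a held-back test sample because that would shrink the derivation sample. It then says: "After deriving the primary base model, we will then use 10-fold cross validation to evaluate the predictive accuracy of the candidate final model".

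The Protocol nowhere says that screening or selection is repeated within the folds, and it describes no other internal or external validation. The number of candidates is not given; Section 4.1 says only that "PROP is a hypothesis generating multicenter study with myriad candidate predictors".

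**The concern.** Cross-validation gives an honest accuracy only if the held-out infants played no part in building the model that is tested on them. Here the order (derive, then validate) and the object (a candidate model already chosen) mean that all infants contributed to the choice of predictors. Refitting the coefficients without one tenth of the infants does not undo that choice. A marker that entered because of a chance association in the full cohort carries much of that association into each held-out fold.

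The primary hypothesis concerns prediction. The first specific aim (Section 2.2) is to predict respiratory disease more accurately than current BPD diagnoses, and Section 4.3.4 plans that comparison. The BPD definitions are set in advance and undergo no selection, so the optimism would fall on the new model alone.

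**Working it through.** **Inputs.** Section 4.4.1: "For a PRD rate of 40%, given a sample size of 750 and a conservative missing rate of 10"%, hence n = 750 × 0.90 = 675. The same section claims: "we will have sufficient power (>80%) to detect a significant biomarker-PRD association at OR of 1.25 or higher" per SD. Section 4.6: "Most standard hypothesis tests will be specified as using a two-sided significance level" of 0.05. The number of candidates is an assumption, varied from 10 to 200.

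**Step 1: reproduce the plan's own figure.** The Protocol states no accuracy figure, so its power statement serves to confirm n and the event rate. For one standardised predictor in logistic regression:

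power = Φ(√(n p(1−p)) × ln OR − 1.960) = Φ(√(675 × 0.40 × 0.60) × ln 1.25 − 1.960) = Φ(12.728 × 0.2231 − 1.960) = Φ(0.880) = 0.811.

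This agrees with the stated power above 80%.

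**Step 2: no marker predicts PRD.** Each run draws 675 infants with 40% PRD and K independent normal markers unrelated to PRD. Selection is a univariate screen at p≤0.20, then backward removal until all remaining terms have p<0.10. Three mean AUCs are compared: apparent (no validation); selection once on all infants, then 10-fold cross-validation that only refits coefficients; and selection repeated inside each training fold. The true value is 0.50. Runs per row: 200, 200, 150, 60 and 15.

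| K | Markers kept | Apparent AUC | CV after selection | Selection inside folds |
|---|---|---|---|---|
| 10 | 0.9 | 0.532 | 0.530 | 0.499 |
| 20 | 2.1 | 0.561 | 0.554 | 0.502 |
| 50 | 5.2 | 0.604 | 0.584 | 0.503 |
| 100 | 10.7 | 0.652 | 0.621 | 0.505 |
| 200 | 21.5 | 0.711 | 0.664 | 0.503 |

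At K = 50 the optimism falls from 0.604 − 0.50 = 0.104 to 0.584 − 0.50 = 0.084. Cross-validation in the stated order therefore removes 0.020/0.104, about a fifth of it.

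**Step 3: vary the selector.** Backward removal at p<0.10 is only one version of the plan, so the final threshold was changed to match AIC (drop a term if its χ² on 1 df is below 2) and BIC (below ln 675 = 6.51). Mean AUC with cross-validation after selection, no true predictors:

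| Final selector | K = 30 | K = 50 | K = 100 |
|---|---|---|---|
| p<0.10 | 0.56 | 0.58 | 0.62 |
| AIC-equivalent | 0.57 | 0.58 | 0.62 |
| BIC-equivalent | 0.51–0.52 | 0.52 | 0.55 |

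Selection inside the folds gives about 0.50.

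**Step 4: true predictors present.**

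- Five true markers at OR 1.25 per SD among 50 or 100 candidates (25 runs each, p<0.10): cross-validation after selection reports 0.641 or 0.671. The AUC in a new sample of 20,000 is 0.595 or 0.581, and the nested estimate is 0.594 or 0.585.
- Three true covariates always kept, the other candidates noise: the post-selection estimate exceeds the nested one by about 0.03 to 0.08 with p<0.10 or AIC-like selection, and by about 0.005 to 0.02 with BIC-like selection.

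**Step 5: the Section 4.6.4 wording.** Testing 50 null markers once each at 0.05 gives 50 × 0.05 = 2.5 false positives on average. After the screen and removal to p<0.10, about 3.0 of the retained markers have p<0.05. Selection at these thresholds offers no protection against false positives.

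**The case against.** **The Protocol does not forbid repeating selection in each fold.** This is true, and fold-level detail can be left to an analysis plan. But Section 4.9 is not silent: it states an order and names the already selected model as what is evaluated. Followed as written, that procedure gives a biased figure.

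**The size depends on choices the Protocol leaves open.** This stands. With BIC-like selection and 10 null candidates the mean AUC is only 0.506. Markers carried forward on literature support add no optimism through the screen. LASSO itself, correlated markers and the random nursery effect were not simulated.

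**A global null is unrealistic.** Section 4.6.2 adjusts for gestational age, birth weight and other covariates, and Section 2.3 says risk falls with gestational age. A reader might infer that the plan will show discrimination where none exists; the documents do not support that, because some true prediction is expected. With three true covariates giving a base AUC of about 0.69, adding 30, 50 or 100 noise candidates raises the reported AUC above that base by only about 0.009, 0.013 or 0.026 (p<0.10), or 0.003, 0.002 or 0.009 (BIC). The gap to the nested estimate is larger, because the noise markers also worsen true prediction. That gap is the relevant one for judging the model actually reported.

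**The cross-validated AUC is not the test of the primary hypothesis.** A reader might assume it is. The Protocol does not say so: Section 4.4.1 bases power on odds ratios, and Section 4.6.4 reports significance values for odds ratios.

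**The study is openly hypothesis generating.** Section 4.6.4 gives reasons for avoiding severe multiplicity adjustment, and that policy is a legitimate trade-off. It justifies liberal screening, but not a biased estimate of accuracy.

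**Conclusion.** Wrong as written. On the plain reading of Sections 4.6.1, 4.6.4, 4.7.1 and 4.9, the held-out folds are not independent of model building, so the cross-validated accuracy is biased upward and keeps most of the optimism due to selection. At n = 675 and 40% PRD, with 30 to 100 candidates and no true predictor, the mean AUC is about 0.56 to 0.62 with p<0.10 or AIC-like selection and about 0.51 to 0.55 with BIC-like selection, instead of 0.50. With strong covariates forced in, the excess over the nested estimate is roughly 0.005 to 0.08.

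The direction is firm. The size rests on an assumed number of independent candidates and on threshold-based stand-ins for the listed selectors. The tilt in the comparison with BPD follows from the reasoning but was not simulated. The claim in Section 4.6.4 that stepwise selection protects against false positives is a secondary fault of wording.

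**What to change.** State in Section 4.9 that the complete data-driven process is repeated within each of the 10 training folds: univariate screening, stepwise, AIC, BIC or LASSO selection, any tuning, and the choice of interactions and ROC cut-offs. State also that accuracy is computed from out-of-fold predictions only. A bootstrap optimism correction that covers the whole process would be an acceptable alternative.

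The final model is still derived on all infants, so the Protocol's reason for declining a held-back sample does not apply. The cost is wording, computing time and a lower reported accuracy; no new data are needed.

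Secondary: soften or delete the statement in Section 4.6.4 that stepwise selection at p<0.15 and p<0.10 protects against false positives. Reporting false-discovery-rate q-values beside the raw p-values is optional and not part of the required change.
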